## Protocol Summary

---

**Study Compound(s):** BOTOX® (OnabotulinumtoxinA) Purified Neurotoxin Complex

---

**Phase:** IV

**Study Objective(s):** To evaluate the efficacy and safety of BOTOX 100 U (onabotulinumtoxinA), compared to placebo, when injected into the bladder using an alternative injection paradigm (2 trigonal and 8 peri-trigonal injections) in reducing the number of daily urinary incontinence episodes in patients with overactive bladder (OAB) and urinary incontinence whose symptoms have not been adequately managed with an anticholinergic.

---

**Key Clinical Hypotheses:**

- BOTOX 100 U is more effective compared to placebo, when injected into the bladder using the alternative paradigm (2 trigonal and 8 peri-trigonal injections), in reducing the number of daily urinary incontinence episodes from baseline at Week 12.
- BOTOX 100 U has an acceptable/better safety profile, including the risk of incomplete bladder emptying and need for clean intermittent catheterization (CIC), when administered as 10 injections into the lower part of the bladder (2 trigonal and 8 peri-trigonal) of patients with OAB with urinary incontinence.

### Study Design

*Structure:* Multicenter, randomized, double-blind, placebo-controlled, parallel-group

*Duration:* Patients will participate in the study until the following study exit criteria are met:

- Completion of 30 weeks post Randomization/Day 1, and
- If a second injection was received, at least 12 weeks post-treatment follow-up after Treatment 2.

Therefore, for full study participation, patients will be expected to participate in the study for a minimum duration of 25 weeks (ie, if patient qualifies for second treatment at Week 12 clinic visit and proceeds to second treatment) and a maximum duration of approximately 53 weeks (ie, if a patient requested and qualified for Treatment 2 at Week 30, received an injection at Week 34, and completes other study visits at the maximum allowable visit window).

*Study Treatment Group:* BOTOX 100 U Injection

*Control:* Placebo (saline) Injection

*Dosage/Dose Regimen:* All patients will receive a study treatment on Day 1 following fulfillment of all of the Day of Treatment Criteria. An additional treatment may also be administered following fulfillment of pre-specified qualification for Treatment 2 criteria and Day of Treatment Criteria.

### Study treatment

Treatment of BOTOX 100 U or placebo will be administered as 10 injections each of 0.5 mL, 8 into the lower portion of the posterior wall of the bladder and 2 into the trigone, via cystoscopy.

**Treatment 1:**

All eligible patients who meet inclusion/exclusion criteria will receive their first treatment with BOTOX 100 U or placebo after randomization on Day 1. All Day of Treatment Criteria must be fulfilled prior to the injection procedure.

## Day of Treatment Criteria:

- Central laboratory urinalysis results and, if applicable, urine culture and sensitivity results for possible urinary tract infection (UTI) from Screening have been reviewed
- Negative urine dipstick reagent strip test (for nitrites and leukocyte esterase (WBC)) on the day of Treatment.
- Patient is asymptomatic for a UTI on the day of treatment, in the opinion of the investigator.
- Patient has discontinued any antiplatelet or anticoagulant therapy or medications with anticoagulative effects 3 days prior to treatment. Some medications may need to be withheld for > 3 days per clinical judgment of the investigator.
- Negative urine pregnancy test for women of childbearing potential on the day of Treatment 1.
- Patient has initiated appropriate antibiotic medication 1 (approximately 24 hours) to 3 days prior to treatment injection, and will continue it on the day of treatment injection, and for 1 to 3 days after treatment injection (see [Section 5.9.2](#) Prophylactic Antibiotics)
- No symptoms or history of bladder stones or bladder malignancies, based on clinical assessment
- Investigator deems study treatment is medically appropriate and no condition or situation exists which, in the investigator's opinion, puts the patient at significant risk from receiving study treatment

**Treatment 2:**

A second treatment may be administered provided the patient qualifies for Treatment 2 (see below criteria) and only if the Day of Treatment Criteria are fulfilled. All patients will receive BOTOX 100 U for their second treatment. The Qualification for Treatment 2 can occur any time starting at Week 12 up to Week 30 post Treatment 1 and must occur during a clinic visit, either at a regular prescheduled visit or an additional unscheduled visit, depending on the timing of the request for a second treatment. If the patient does not request a second treatment, then the Week 30 clinic visit will be an exit visit.

## Qualification for Treatment 2 criteria:

- Patient must initiate request for Treatment 2.
- Patient experiences  $\geq 2$  episodes of urinary urgency incontinence, with no more than one urgency incontinence-free day, as determined by 3 consecutive days of bladder diary completion in the week prior to the Qualification for Treatment 2 visit.

- Post-void residual (PVR) urine volume must be < 200 mL at the Qualification for Treatment 2 visit.
- Investigator deems that Treatment 2 is medically appropriate and no condition or situation exists which in the investigator's opinion, puts the patient at significant risk from receiving a second treatment.
- A minimum of 12 weeks must have elapsed since Treatment 1.

[figure not shown]
Once these criteria have been met, the patient will be considered qualified for Treatment 2.

[figure not shown]
Treatment 2 administration should occur within 28 days of the Qualification for Treatment 2 visit. The previously described Day of Treatment criteria must be met at the Treatment 2 visit prior to injection.

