## 5.6 Treatment Regimen and Dosing

### 5.6.1 Study Treatments

BOTOX

#### Study Treatment 1

All eligible patients who meet inclusion/exclusion criteria and are enrolled into the study will receive a double-blind treatment of either BOTOX 100 U or placebo for their first study treatment.

The first treatment will be administered after randomization on Day 1 at the investigational site. All Day of Treatment Criteria must be fulfilled prior to treatment administration (see [Section 5.9.1 Day of Treatment 1 Criteria](#)).

#### Study Treatment 2

All patients can request and potentially qualify for a second treatment, and if the qualification criteria are met (Qualification for Treatment 2 Criteria provided in [Section 5.10.1 Request/Qualification for Treatment 2](#)) they will receive BOTOX 100 U for their second treatment.

Administration of Treatment 2 should occur within 28 days of the qualification for Treatment 2 visit. Patients must fulfill the ‘Day of Treatment 2 Criteria’ prior to Treatment 2 administration (see [Section 5.10.2 Day of Treatment 2 Criteria](#)). Treatment 2 must not be administered before 12 weeks after Treatment 1.

The reason(s) for the patient requesting retreatment will be collected at each visit in which the request is made, regardless of whether the patient qualifies for Treatment 2 at that visit or not.

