### **5.9.2 Prophylactic Antibiotics**

Prophylactic antibiotics are to be administered beginning 1 (approximately 24 hours) to 3 days before study treatment, on the day of study treatment, and continuing for 1 to 3 days after study treatment. The investigator is to prescribe the appropriate antibiotic and number of days pretreatment and post treatment based on clinical judgment and local site practice.

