## **5.10        Retreatment**

### **5.10.1      Request/Qualification for Treatment 2**

Patients may request Treatment 2 at the Week 12 clinic visit or any time thereafter up to Week 30. A qualification visit will be added to the patient's schedule if the request for retreatment is made outside the regular prescheduled visits. A clinic visit (prescheduled or unscheduled) at which the patient is assessed after making a request for a second treatment will then become a Qualification for Treatment 2 visit, and is no longer considered the post-treatment visit, and the appropriate eCRFs should be completed. Treatment 2 should occur within 28 days of qualification and no later than Week 34 (+/-7 days). The patient must meet all qualification criteria before Treatment 2 can occur.

The 'Qualification for Treatment 2 Criteria' are:

- Patient must initiate request for Treatment 2
- Patient experiences  $\geq 2$  episodes of urinary urgency incontinence, with no more than 1 urgency incontinence-free day, as determined by the 3 consecutive days of bladder diary completion in the week prior to the qualification for Treatment 2 visit (ie, Week 12, 24 or 30 post Treatment 1 or an additional visit, depending on the timing of the retreatment request).
- PVR urine volume must be  $< 200$  mL.
- Investigator deems that Treatment 2 is medically appropriate and no condition or situation exists which, in the investigator's opinion, puts the patient at significant risk from receiving a second treatment.
- A minimum of 12 weeks must have elapsed since Treatment 1.

Once a patient has met the 'Qualification for Treatment 2 Criteria', the patient is considered qualified for Treatment 2 and may proceed with the treatment visit (see [Section 5.10.2](#)). The Treatment 2 visit may occur on the same day of qualification or may be scheduled on another day if the Treatment 2 criteria are not met. If the Treatment 2 visit is rescheduled, visit procedures for which the patient has already been qualified do not need to be repeated.

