### **5.10.2 Day of Treatment 2 Criteria**

A patient should be treated within 28 days of the Qualification for Treatment 2 visit, once all Treatment 2 criteria are met. If the patient does not meet all Treatment 2 criteria at the time of the visit, the treatment visit may be rescheduled within the 28-day window to allow for treatment criteria to be met.

The 'Day of Treatment 2 Criteria' are:

- Urine culture and sensitivity results for possible UTI have been reviewed from Qualification, if applicable.
- Negative urine dipstick reagent strip test (for nitrites and leukocyte esterase (WBC)).
- Patient does not have a UTI.
- Appropriate prophylactic antibiotic coverage has been initiated, and patient understands to continue the antibiotics following the procedure (see [Section 5.9.2](#) Prophylactic Antibiotics)
- Antiplatelet or anticoagulant therapy or medications with anticoagulative effects have been discontinued at least 3 days prior to study treatment (see [Section 4.5.1](#)).
- Negative urine pregnancy test result (for women of childbearing potential)
- Investigator continues to deem study treatment is appropriate and no condition or situation exists which, in the investigators opinion, puts the patient at significant risk from receiving Treatment 2.

Note: Urine culture and sensitivity results need to be available and required prophylactic antibiotics need to have been initiated before Treatment 2 is administered (please refer to [Section 5.9.2](#)).

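### The synopsis applies the Treatment 1 day-of-treatment checklist to Treatment 2, Section 5.10.2 gives a different checklist, and 5.10.2 is unclear on when a culture result is needed

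*Protocol*

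**What the plan says.** The Protocol Summary contains one list of Day of Treatment Criteria. Its paragraph on Treatment 2 makes the second injection conditional on that list, and its Qualification for Treatment 2 text repeats this: "The previously described Day of Treatment criteria must be met at the Treatment 2 visit prior to injection". Among other items, the list requires that "urine culture and sensitivity results for possible urinary tract infection (UTI) from Screening have been reviewed", that the patient has no UTI symptoms in the investigator's opinion, and "No symptoms or history of bladder stones or bladder malignancies, based on clinical assessment". Its pregnancy test item is tied to the day of Treatment 1.

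The body of the protocol uses a separate list. Section 5.6.1 states: "Patients must fulfill the ‘Day of Treatment 2 Criteria’ prior to Treatment 2 administration", and points to 5.10.2. There the urine item reads "Urine culture and sensitivity results for possible UTI have been reviewed from Qualification, if applicable", the UTI item requires that the patient has no UTI, and no item names stones or malignancy. A note under the list adds: "Urine culture and sensitivity results need to be available and required prophylactic antibiotics need to have been initiated before Treatment 2 is administered".

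On timing, Section 5.10.1 says "The Treatment 2 visit may occur on the same day of qualification", and provides for another day if the Treatment 2 criteria are not met.

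**The concern.** The synopsis and 5.10.2 both claim to state what must be checked before the second injection, and they do not state the same thing. No passage says which governs. With approximately 50 sites, some staff could work from the synopsis and others from 5.10.2. The checks concerned are infection and bladder-pathology checks before an invasive bladder injection, so the same patient could be injected under one list and deferred under the other.

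The culture wording adds a second uncertainty. A site that qualifies a patient and wishes to treat on the same day needs to know whether a culture result must be in hand for every patient or only where a culture was triggered. Section 5.10.2 can be read either way.

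**Working it through.** The plan states no figure on this point, so the check is a comparison of passages plus simple day counts.

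**Step 1. Qualification criteria.** The Protocol Summary and Section 5.10.1 give the same five items: patient request, diary threshold, PVR limit, investigator judgement, and at least 12 weeks since Treatment 1. There is no conflict here.

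**Step 2. Day-of-treatment criteria.**

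| Item | Protocol Summary list | Section 5.10.2 list | Same check? |
|---|---|---|---|
| Source of urine results | Screening | Qualification | No |
| Central urinalysis review | Named | Not named | No |
| UTI status | No symptoms | No UTI | No |
| Stones/malignancy | Named bar | Not named | No |
| Pregnancy test | Day of Treatment 1 | Negative result required | Wording differs; Section 6.3.11 requires a test on the day of Treatment 2 |
| Dipstick | Negative | Negative | Yes |
| Antibiotics | Refers to 5.9.2 | Refers to 5.9.2 | Yes |
| Anticoagulant stop | 3 days | At least 3 days | No material difference |
| Investigator judgement | Present | Present | Yes |

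The UTI row is a difference in substance if the definition in Section 9.1.2 is carried over. That section records a UTI on culture and leukocyte counts whether or not there are symptoms. A patient who meets those counts, has no symptoms and has a negative dipstick would pass the synopsis item and fail the 5.10.2 item. Section 5.10.2 does not cite 9.1.2, so carrying the definition over is an assumption.

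The stones/malignancy row is narrower than it looks. Section 5.9.1 already applies that item at Treatment 1, so only findings made afterwards matter. For malignancy, Section 8.9 says that patients with a new or recurrent malignancy, other than basal cell carcinoma, should be discontinued and/or receive no further study treatment. What remains unnamed in 5.10.2 is chiefly new bladder stones, which are left to investigator judgement.

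**Step 3. Culture wording in 5.10.2.** Section 6.3.10 orders a culture only when the central laboratory urine result suggests a UTI. A patient with a clean urinalysis therefore has no culture. The bullet allows for this; the note, read as written, does not.

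**Step 4. Same-day treatment.** Take the Qualification day as day 0, with treatment also on day 0.

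- Antibiotics: Section 5.9.2 says "Prophylactic antibiotics are to be administered beginning 1 (approximately 24 hours) to 3 days before study treatment". The start must fall between 0 − 3 = day −3 and 0 − 1 = day −1.
- Anticoagulants: 5.10.2 requires a stop at least 3 days earlier, so no later than 0 − 3 = day −3.

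Both steps come before qualification is confirmed, so same-day treatment needs a patient prepared in advance. If a culture result is required for everyone, or is triggered at that visit, it must also be available that day. The documents give no laboratory turnaround time.

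**Step 5. Window.** Week 30 + 28 days = Week 34, which agrees with 5.10.1.

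**The case against.** The best defence is that the body is consistent. Sections 3, 5.6.1, 5.10.1 and 6.3.9 of the protocol, and Section 1.1.1 of the SAP, all refer to 5.10.2. The synopsis list plainly reads as a Treatment 1 list, and the amendment summary describes its Screening-urine and stones/malignancy items as criteria for Treatment 1. On this view the synopsis contains a cross-reference slip that a trained site would see through. That stands as evidence of likely intent, and it means divergent practice is possible rather than shown. It does not remove the conflict, because the synopsis expressly applies its list at the Treatment 2 visit.

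Three stronger readings are tempting, and the documents do not support them.

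- **Same-day treatment contradicts the antibiotic, anticoagulant and culture rules.** It does not. The permission in 5.10.1 holds only when the Treatment 2 criteria are met, and 5.10.2 provides rescheduling within 28 days. The request comes before the assessment, so advance preparation is possible.
- **The synopsis would let a site rely on urine results about 40 weeks old.** The sum is 35 days (the limit from screening to a rescheduled Day 1 in 6.3.9) + 34 weeks + 7 days = 35 + 238 + 7 = 280 days = 40 weeks. This is an extreme literal reading. Both lists require a negative dipstick, and 6.3.9 withholds Treatment 2 after a positive one until central results are obtained. Setting 40 weeks against 28 days is also uneven, since from Week 30 to Week 34 plus the same 7-day window is 35 days.
- **UTI rates after Treatment 2 would be distorted.** This is possible but not shown. SAP Section 6 makes no inferential safety comparison, and Section 6.5 assigns events after the second injection to the open-label period.

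The visit schedule (Table 1) is redacted and may settle some timing questions. One is central urinalysis at a Week 24 qualification visit: 5.10.1 allows that visit, while 6.3.10 leaves Week 24 out.

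**Conclusion.** The point holds for the Day of Treatment 2 criteria. Three items differ in substance between the synopsis and 5.10.2 (source of urine results, UTI status, stones/malignancy), and the culture requirement inside 5.10.2 is ambiguous. Sites could therefore apply different checks before the open-label injection.

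The size cannot be put as a number: every retreated patient in either arm falls under one list or the other, and the count of such patients, and of those treated on the qualification day, is not given. Under Section 5.6.1, Treatment 2 cannot be given before 12 weeks, so this wording does not bear on the Week 12 primary comparison.

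A reader might infer that eligibility for retreatment as a whole is contradictory. It is not, because the qualification criteria match. The conclusion assumes that the redacted visit schedule does not state which list governs.

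**What to change.** Reconcile these parts of the protocol: the Day of Treatment Criteria, Treatment 2 and Qualification for Treatment 2 text in the Protocol Summary, and Sections 5.10.1, 5.10.2 and 6.3.10.

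- Have the synopsis point to a single Day of Treatment 2 list, worded identically in the synopsis and in 5.10.2.
- State in that list which UTI item and which stones/malignancy item apply at Treatment 2, and from which visit the urine results are taken.
- Make the culture bullet and the note in 5.10.2 agree with each other and with 6.3.10, so that it is clear when same-day treatment can meet the criteria.

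Which rules stand is for the sponsor's clinical team. The cost is amendment wording and notice to sites. The reconciliation itself calls for no additional patients and no change to the statistical analysis.

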***Randomization:***

Following the screening period, patients who meet the study inclusion/exclusion criteria will be randomly assigned by an interactive web response system (IWRS) to 1 of 2 treatment arms (BOTOX 100 U or placebo) in a 2:1 ratio. One randomization number will be assigned to each patient prior to the first treatment and will be associated with one of the following treatment arms:

- A) BOTOX 100 U
- B) Placebo

**Study Population Characteristics**

*Number of Patients or Subjects:* At least 114 patients will be randomized at approximately 50 sites in the United States (US), in order to achieve 68 patients in the BOTOX 100 U treatment group and 34 patients in the placebo treatment group at the primary time point ie, 102 patients at Week 12 are required. At least 114 patients will be randomized to take into account an attrition rate of 10%.

*Language:* All study materials, whether printed or electronic, including informed consent forms, e-Diary, protocol and all patient and site information will be in the English Language. There are no plans to translate study materials into other languages.

*Condition/Disease:* Patients with symptoms of OAB (frequency and urgency) and urinary incontinence, whose symptoms have not been adequately managed with an anticholinergic.

*Key Inclusion Criteria:* The patient must meet the following key criteria at screening and Randomization/Day 1 in order to be included in the study. These are the key criteria which define the population, not a complete list of all inclusion criteria:

- Patient is male or female, aged  $\geq$  18 years old.
- Patient weighs  $\geq$  40 kg (88 lbs).
- Patient has symptoms of OAB (frequency and urgency) with urinary incontinence for a period of at least 6 months immediately prior to screening, determined by documented patient history.
- Patient understands that they are not to alter their customary life patterns around fluid consumption or micturition while participating in this study.

**Key Exclusion Criteria:** The patient will be excluded from participating in the study for any of the following key criteria assessed during the screening period and Randomization/Day 1, prior to study treatment. These are the key criteria which define the population, not a complete list of all exclusion criteria:

- Patient has symptoms of OAB due to any known neurological reason (eg, spinal cord injury, multiple sclerosis, cerebrovascular accident, Alzheimer's disease, Parkinson's disease, etc.).

- Patient has received pharmacologic therapy to treat symptoms of OAB, including nocturia, within 7 days of the start of the screening period procedures.
- Patient uses CIC or indwelling catheter to manage urinary incontinence.
- Patient has a 24-hour total volume of urine voided > 3000 mL, collected over 24 consecutive hours during the 3-day bladder diary collection period prior to Randomization/Day 1.
- Patient has had previous or current botulinum toxin therapy of any serotype for any urological condition.
- Patient has had previous or current botulinum toxin therapy of any serotype for any non-urological condition within 12 weeks prior to Randomization/Day 1.
- Patient has history or evidence of any pelvic or urological abnormalities, bladder surgery or disease, other than OAB, that may affect bladder function including but not limited to:

- Patient has evidence of urethral and/or bladder outlet obstruction, in the opinion of the investigator, at screening or Randomization/Day 1.
- Patient has a PVR urine volume of > 100 mL at screening. The PVR urine volume measurement can be repeated once; the patient is to be excluded if the repeated measure is above 100 mL.

